11. CRITERIA FOR POSTOPERATIVE VENO-VENOUS HAEMOFILTRATION

To avoid any bias, the need for renal support postoperatively by haemofiltration will follow standard guidelines laid down by the **surgical guidelines** as follows:

Indications for postoperative haemofiltration should be for:

- Hyperkalaemia (6.0 mmol/l) not responding to insulin infusion
- Metabolic acidosis of renal origin
- Anuria or oliguria –20 ml/h for more than 6 hours (despite adequate filling and adequate cardiac output) resulting in clinically significant fluid overload

12. STUDY COMPLIANCE

We do not anticipate any problems with compliance because the treatment will be administered in theatre whilst the patient is under anaesthesia. Once consent is obtained before the operation the patients will not know what treatment allocation they have been

given when they wake up after the operation. There is also no evidence to suggest that patients will be lost during the in-hospital follow-up period or at their routine 6 weeks postoperative follow-up visit.

13. PROPOSED SAMPLE SIZE

Calculation of an accurate samples size at this stage would not be precise since this is a pilot feasibility study. However, existing data accrued from our audit department suggest that, at the Liverpool Heart & Chest Hospital, incident rates for intensive care unit (ICU) stay >3 days for patients with estimated GFR <60 ml/min after isolated coronary artery bypass graft (CABG) surgery in years between 2002 and 2008 were 18%. We estimate that even if the proportion of these patients that stay in ICU for > 3 days is reduced to at least a mean of 12% because of intraoperative haemofiltration, this will be of significant clinical and economic benefit to the NHS. We have estimated that at 80% power (2-sided $\alpha=0.05$), 1112 patients with GFR <60 ml/min will need to be randomised in the main definitive study to detect a reduction in the mean incidents from 18% to 12%. Our plan in this pilot trial is to investigate whether it is feasible to randomise 60 patients in a period of 6 months in a recruitment rate of 10 patients per month from our centre. This complies with previous recommendation for good practice that pilot randomised control trials should recruit a minimum number of 60 patients [24]. The results from this pilot data will allow us to calculate a more accurate sample size and trial duration and/or the number of recruiting centres that would be required for the main trial.

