2. STUDY SUMMARY

Title of study	The Impact of continuous haemofiltration with high volume fluid exchange during cardiopulmonary bypass surgery on the recovery of patients with impaired renal function - A pilot randomised study
Lay title	Impact of blood purification devices on well-being of patients with moderately impaired kidney function and undergoing cardiac surgery
Study design	Single-centre, randomised, prospective clinical trial
No of subjects	60
Study timelines	
Planning, ethics and start-up Mar 2010 – Oct 2010
 
Recruitment Nov 2011 – Mar 2012
 
End of follow-up Mar 2012
 
Analysis and reporting Mar 2012
 
Final report May 2012

Inclusion criteria	Consenting men and women must be at least 18 years old, high-risk patients elective for on-pump coronary artery bypass graft surgery (CABG). They must also have impaired renal function established preoperative by an <60 ml/min measured within 4 weeks before surgery.
Exclusion Criteria	Patients undergoing surgery on the great vessels (aortic surgery) or valve surgery, have significant impaired liver function (serum bilirubin >60 or INR>2 without anticoagulation), patients who are further down the line of renal failure or on-dialysis, have malignancy and those that are pregnant.
Primary outcome measure	Incidents of ICU stay >3 days for patients with renal impairment identified as an estimated glomerular filtration (eGFR) <60 ml/min.
Secondary outcome measures	
Clinical
 
 1. Composite of perioperative incidences: Bleeding, sepsis, death, arrhythmias, stroke, and myocardial infarction 2. Need for postoperative continuous veno-venous haemofiltration (CVVH) in the ICU- Indications for requirement of postoperative continuous veno-venous haemofiltration must adhere to our surgical guidelines. 3. Mechanical ventilation time 4. Hospital stay 5. eGFR at 6 weeks follow-up 
Secondary Economic Outcomes: Resource utilisation associated with each of the two pilot arms such as: ICU stay and hospital stay, mechanical ventilation, medications, tests and procedures undertaken until the end of the follow-up period.

Follow-up	Outcome measures will be assessed until hospital discharge or 28 days, whichever is sooner and at 6 weeks follow-up appointment
-----------	---

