3. FLOW DIAGRAM

4. RESEARCH OBJECTIVES

There is a widespread variability in clinical practice within cardiac surgery units worldwide on the use of haemofiltration on a case-by-case basis, the impact and safety of this modality however, is unknown. In addition, no evidence exists to suggest that haemofiltration as applied to patients during the period of the operation may have an impact upon the postoperative cost of care and clinical renal impairment outcomes. We hypothesise that the initiation of intraoperative haemofiltration with high-volume fluids exchange during cardiopulmonary bypass in patients with impaired renal function effectively reduces overall length of intensive care unit (ICU) stay and progression of renal impairment. Since no large randomised trial has undertaken this kind of study before, the design of the study is limited by the absence of past trial data that could be used as a reference. In order to overcome these limitations we propose to at first conduct a pilot feasibility study with the following objectives:

1. To assess the feasibility of randomising 60 patients with impaired kidney function (eGFR<60 ml/min) undergoing coronary artery bypass surgery in 6 months within a single-centre for intraoperative haemofiltration i.e. to investigate the likely recruitment rates and issues that may impact recruitment into the study.
2. To assess the suitability and reliability of the outcome measures.
3. To investigate the likelihood of recruitment into the main definitive study and explore issues that may impact recruitment such as staff requirements, barriers to recruitment, suitability and reliability of the outcome measures selected.

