5.3 WHY THE TRIAL IS NECESSARY?

This pilot study aims to assess the feasibility of randomising 60 coronary artery bypass surgery patients with impaired kidney function in 6 months within a single-centre for

intraoperative haemofiltration. This should allow us to investigate the likelihood of recruitment into the main definitive study and explore issues that may impact recruitment such as likely patient numbers, staff requirements, and barriers to recruitment, suitability and reliability of the outcome measures selected. In the financial year 2008-2009, up to 90 patients that would meet the inclusion criteria of the study were operated at our centre. We predict that it is highly probable that more than 100 patients that meet our inclusion criteria will be operated in the financial year 2010-2011 which is our target recruitment period. Specifically, the results will be useful in giving a preliminary indication of the impact the procedure has on healthcare pathways such as the intensive care and hospital stays since renal impairment is one of the major complications for patients undergoing cardiac operations.

Furthermore, the results of the pilot trial will begin to tell us whether a definitive randomised trial can address the underlying concerns about costs and benefits (i.e. value) of using intraoperative haemofiltration. Currently, the cost of an intraoperative haemofiltration is approximately £200 a patient which is only 3-4% of what it would cost to perform postoperative continuous veno-venous haemofiltration or dialysis in intensive care units (ICU)/high-dependent units (up to £5000-£6000 a patient over and above standard costs). If the pilot study can establish that the definitive trial can give clear evidence whether intraoperative haemofiltration for patients with renal impairment is effective at reducing the likelihood of postoperative haemofiltration, length of stay in ICU and hospital this will represent an important treatment strategy that could save the NHS millions of pounds every year. Thus there is potential for the main definitive study to influence clinical decision making, identify the level of care required to reduce length of stay in ICU and hospital for patients, improve overall operative outcomes and reduce treatment costs.

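### The target of 60 patients in 6 months exceeds the centre's own counts of eligible patients, and the recruitment dates conflict

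*Protocol*

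**What the plan says.** The first objective in Section 4 of the protocol is "To assess the feasibility of randomising 60 patients with impaired kidney function (eGFR<60 ml/min) undergoing coronary artery bypass surgery in 6 months" at a single centre. Section 5.3 repeats the target. Section 13 gives it as "Our plan in this pilot trial is to investigate whether it is feasible to randomise 60 patients in a period of 6 months" and puts the monthly rate at 10 for this one centre.

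Section 5.3 holds the only information on supply. For the past it says "In the financial year 2008-2009, up to 90 patients that would meet the inclusion criteria of the study were operated at our centre". For the future it says "it is highly probable that more than 100 patients that meet our inclusion criteria will be operated in the financial year 2010-2011", and it names that year as the target recruitment period.

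The timelines in Section 2 list recruitment as "Nov 2011 – Mar 2012", with follow-up also ending in March 2012 and start-up ending in October 2010. Sections 2 and 15 both include a six-week follow-up visit, which Section 15 counts from discharge.

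Section 13 says the pilot results will be used to set the sample size, duration and/or number of centres of the main trial. Section 21.3 says that the number of eligible patients and the proportion of them randomised will be recorded.

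**The concern.** The stated monthly rate is higher than the monthly number of eligible patients that the same protocol reports, and that holds before anyone declines. The counts refer to the inclusion criteria only, and Section 5.3 does not say whether the exclusions in Section 7.5 had been applied. Section 2 then shortens the window to five months and places it in a different year from Section 5.3.

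Recruitment is what this pilot is mainly meant to learn about. A benchmark above the documented supply mixes two reasons for a shortfall, too few eligible patients and unwillingness to take part. These have different consequences for the duration and number of centres of a main trial that Section 13 puts at 1112 patients.

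**Working it through.** **Inputs.** 60 patients, 6 months, 10 a month (Sections 4, 5.3, 13); at most 90 eligible in 2008-2009 and more than 100 forecast for 2010-2011 (Section 5.3); recruitment November 2011 to March 2012 (Section 2); six-week visit (Sections 2, 15). No consent rate is given, so 70% and 50% below are assumptions.

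**The plan's own rate.** 60 / 6 = 10.0 a month, as stated.

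**Supply per month.** 90 / 12 = 7.5 (a ceiling for 2008-2009). 100 / 12 = 8.33 (a floor for the 2010-2011 forecast).

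**Supply over the window, and the share of it that 60 patients would need.**

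| Eligible per year | Eligible in 6 months | 60 as a share | Eligible in 5 months | 60 as a share |
|---|---|---|---|---|
| 90 | 45.0 | 133% | 37.5 | 160% |
| 100 | 50.0 | 120% | 41.7 | 144% |
| 110 | 55.0 | 109% | 45.8 | 131% |
| 120 | 60.0 | 100% | 50.0 | 120% |

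Break-even at full consent is 60 × 12 / 6 = 120 eligible a year for six months, a third above the 2008-2009 ceiling (120 / 90 = 1.33). At an assumed 70% consent it is 120 / 0.7 = 171 a year.

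**Chance variation.** If the number of eligible patients in the window is Poisson (an assumption, not in the protocol) and all consent, the chance that it reaches 60 in six months is 1.9% at 90 a year, 9.2% at 100, 27% at 110 and 52% at 120.

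**Time needed for 60 patients**, 60 / (monthly supply × consent).

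| Consent | 90 a year | 100 a year |
|---|---|---|
| 100% | 8.0 months | 7.2 months |
| 70% (assumed) | 11.4 months | 10.3 months |
| 50% (assumed) | 16.0 months | 14.4 months |

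**Dates.** November to March, counted inclusively, is 5 months, which would need 60 / 5 = 12 a month. That window lies outside financial year 2010-2011 and starts a year after the end of start-up. If follow-up really ends on 31 March 2012, a visit six weeks after discharge means that randomisation must stop by 18 February 2012 at the latest. That leaves about 3.6 months from 1 November 2011, and 27 to 30 eligible patients at 90 to 100 a year.

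**The case against.** Several stronger readings are tempting, and the protocol does not support them.

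- **The pilot must fail its first objective.** A reader might infer this from the arithmetic. The objective is to assess whether 60 in six months is feasible and to learn the likely recruitment rate. A pilot that recruits fewer still answers that. Missing a target is not failing to assess it.
- **The target is impossible.** The forecast is of more than 100, which is a floor. A supply of 120 a year would satisfy it and would give 60 in six months. This stands as logic, but it needs every eligible patient to consent, and no figure in the protocol points to 120.
- **A missed target would trigger a wrong decision to stop.** No progression threshold is stated. The results feed into the duration and number of centres, and a low observed rate would inform both.
- **A shortfall would hide the consent rate.** It would not, because Section 21.3 already provides for recording the proportion of eligible patients randomised.
- **The five-month figures show a worse shortfall.** They rest on a date that may be a slip. If recruitment was meant to start in November 2010 and run to March 2012, that is 17 months and about 128 to 142 eligible patients (17 × 7.5 and 17 × 8.33), of whom 60 is 42% to 47%. The eligible counts also belong to other years than the listed window. The dates are therefore something to reconcile, not evidence about feasibility.

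It is also fair to say that none of this biases the comparison between the arms or affects safety. What remains is that the stated rate is above every supply figure in the document, and that the dates cannot all be right.

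**Conclusion.** The concern holds in this form: 10 a month is not supported by the centre's own eligible counts of at most 7.5 a month observed and a forecast minimum of about 8.3. Over six months, 60 patients would need 120% to 133% of the eligible patients at those figures, before refusals and possibly before exclusions. The target is very likely to be missed, but a shortfall would still be informative.

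This rests on supply being near the figures in Section 5.3. It would change only with documented evidence of at least 120 eligible patients a year and near-complete consent. The shortfall does not depend on the Poisson model or on the assumed consent rates, which only show its likely size.

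Separately, the recruitment dates in Section 2 contradict the six-month window in Sections 4, 5.3 and 13 and the recruitment year in Section 5.3. They also leave no room for the six-week visit of patients randomised late in the window.

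**What to change.** Keep the 60 patients, since Section 13 justifies that number as a recommended minimum for pilot trials, and change the rate and the window.

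1. In Sections 2, 4, 5.3 and 13, state one recruitment rate and one window consistent with the eligible counts and an explicit consent assumption. At 90 to 100 eligible a year, the window is at least 7.2 to 8 months at full consent, about 10 to 11 months at an assumed 70%, and about 14 to 16 months at an assumed 50%. If the sponsor has evidence of higher supply, give it, and say whether the counts are net of the exclusions.
2. Reconcile the dates: the start and end of recruitment, the financial year in Section 5.3, the end of start-up, and an end of follow-up that leaves room for the last patient's six-week visit.
3. Judge feasibility on the proportion of eligible patients randomised, already to be recorded under Section 21.3, with a 95% confidence interval, alongside patients per month. A shortfall can then be traced to supply or to consent.

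The cost is an amendment and a longer stated recruitment window, with the staff time that a longer window takes on a grant-funded pilot. No extra patients or procedures are needed.

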14. STUDY OUTCOMES

Proposed Outcome Measures: These will be evaluated for suitability and reliability for the main trial - Our chosen primary outcome and secondary outcome measures will be monitored to ensure they are suitable and reliably informative of the impact of intraoperative haemofiltration. There is an element of concern that the outcomes could be confounded by crossovers between the experimental groups, in response to protocol deviation by clinicians. All protocol deviations will be documented in the database. The primary analysis will be completed on an intention to treat basis but separate information will be provided on the incidence and rate of protocol deviation and crossover. We will also report a range of other outcomes including key measures of resource utilisation and kidney function at 6 weeks follow-up to establish whether these may be suitable for the main trial. The outcome measures to be evaluated are:

PRIMARY OUTCOMES

Incidents of ICU stay >3 days for patients with renal impairment identified as an estimated glomerular filtration (eGFR) <60 ml/min.

SECONDARY OUTCOMES

CLINICAL OUTCOMES

- Composite of perioperative incidences: Bleeding, sepsis, death, arrhythmias, stroke, and myocardial infarction
- Need for postoperative continuous veno-venous haemofiltration (CVVH) in the ICU - Indications for requirement of postoperative continuous veno-venous haemofiltration must adhere to our **surgical guidelines**.
- Mechanical ventilation time
- Hospital stay
- eGFR at 6 weeks follow-up

SECONDARY ECONOMIC OUTCOMES: Resource utilisation and key costs indicators associated with each of the two pilot arms specifically ICU stay and hospital stay, postoperative renal replacement therapy, mechanical ventilation, medications, will be estimated up until hospital discharge. Participants will be required to complete health-related quality of life questionnaire EQ-5D at hospital admission before surgery and at the 6 weeks follow-up hospital visits.

15. FOLLOW UP DATA COLLECTION

1. Follow-up will be during the in-hospital stay phase and at 6 weeks post-discharge follow-up visit.
2. All information will be collected in structured Case Record Forms (CRFs).
3. A Manual of Operation documents containing relevant procedural instructions and definitions will be produced.
4. Data will be entered into a secure password protected database.
5. Prospective monitoring of adverse and clinical events will start at randomisation and will continue until hospital discharge
6. Costs associated with each of the two pilot arms, postoperative renal replacement therapy, ICU stay and hospital ward stay, and medications will be estimated up until hospital discharge.

7. Prospective monitoring of serious adverse and clinical events will start at randomisation and will continue until hospital discharge.

16. PLANNED ANALYSES

Intention to treat will be considered as the primary analysis. The clinical and economic impact of intraoperative haemofiltration versus no haemofiltration treatment will be examined. Analysis of the primary endpoint and other continuous data will be performed by using a 2-sided unpaired t-test or an equivalent non-parametric test. Categorical secondary outcome measures will be examined using a Chi-square test or Fisher's exact test as required. The potential cost differences per patient will be estimated with confidence intervals. Exploratory analysis will be undertaken using Bayesian Value of Information methods described by Tan and Smith [25] that balances the benefit of detecting a minimally significant difference with at least a given power against the costs of the patient sample size and/or the risk that the research poses to patients. The result of this analysis will provide guidance on the optimal sample size to use in a future RCT that would seek to evaluate the impact of haemofiltration on healthcare costs.

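### Section 16 assigns the yes/no primary endpoint (ICU stay >3 days) a test for continuous data, although the protocol defines it and sizes the main trial on it as a proportion

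*Protocol*

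**What the plan says.** Section 14 names one primary outcome: "Incidents of ICU stay >3 days for patients with renal impairment identified as an estimated glomerular filtration (eGFR) <60 ml/min". The study summary (Section 2) says the same. Each patient either has the event or does not.

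Section 13 treats this outcome as a proportion. It gives the audit rate ("surgery in years between 2002 and 2008 were 18" per cent) and sizes the definitive trial at 1112 patients with 80% power and two-sided alpha 0.05, "to detect a reduction in the mean incidents from 18% to 12" per cent.

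Section 16 classes the endpoint differently: "Analysis of the primary endpoint and other continuous data will be performed by using a 2-sided unpaired t-test or an equivalent non-parametric test". The next sentence reads: "Categorical secondary outcome measures will be examined using a Chi-square test or Fisher's exact test as required". No other section assigns a proportion-based analysis to the primary endpoint.

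Section 4 states the hypothesis as a duration, namely that the intervention "effectively reduces overall length of intensive care unit (ICU) stay and progression of renal impairment". Section 5.2 likewise speaks of reducing the duration of ICU stay. ICU stay also appears among the secondary economic outcomes in Sections 2 and 14, but not in the list of clinical outcomes.

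**The concern.** In the Section 16 sentence, the word *other* places the primary endpoint among the continuous variables. The sentence after it confines the tests for categorical data to secondary outcomes. An analyst who follows both would compare mean or ranked ICU days and report that as the primary result.

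That is a different quantity from the one in Section 14. A t-test on days estimates a difference in mean days, and a rank test addresses a shift in the distribution. Neither is the difference in the proportion staying beyond 3 days, which is the quantity the 18% and 12% describe. Section 13 says the pilot results will be used to refine the main-trial sample size. The useful output for that is the event proportion per arm with a confidence interval, and Section 16 does not ask for it.

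Sections 4 and 5.2 speak of duration while Sections 2, 13 and 14 speak of the event, so the protocol supports two candidates for what is primary.

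**Working it through.** **Step 1. Does the main-trial size treat the endpoint as binary?**

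Inputs from Section 13: p1 = 0.18, p2 = 0.12, power 80%, two-sided alpha 0.05. Allocation is taken as 1:1, inferred from the balanced blocks in Section 9.

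Pooled two-proportion formula without continuity correction:

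n per arm = [z(0.975)·√(2·p̄·(1−p̄)) + z(0.80)·√(p1(1−p1) + p2(1−p2))]² / (p1−p2)²

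- p̄ = 0.15, so 2 × 0.15 × 0.85 = 0.255
- 0.18 × 0.82 + 0.12 × 0.88 = 0.1476 + 0.1056 = 0.2532
- [1.960 × √0.255 + 0.8416 × √0.2532]² = 1.4132² = 1.9972
- 1.9972 / 0.06² = 1.9972 / 0.0036 = 554.8, so 555 per arm and **1110 in total**, against 1112 stated

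| Variant | Per arm | Total |
|---|---|---|
| Pooled, two-sided | 555 | 1110 |
| Unpooled, two-sided | 553 | 1106 |
| Arcsine, two-sided | 551 | 1102 |
| Continuity-corrected, two-sided | 588 | 1176 |
| Pooled, one-sided | 437 | 874 |

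The stated figure is an ordinary comparison of two proportions. A t-test on days would need a mean difference and a standard deviation. The protocol gives neither, so 1112 cannot be derived for that analysis.

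**Step 2. What if the t-test is run on ICU days?**

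The estimate is then in days. It can be computed, but it is not the Section 14 outcome, and it has no counterpart in the Section 13 calculation.

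**Step 3. What if the t-test is run on the 0/1 indicator?**

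The mean of a 0/1 variable is the event proportion, so the difference in means is the risk difference. With N patients in total, t² = χ²(N−2)/(N−χ²), where χ² is the uncorrected Pearson statistic. For N = 60 the t critical value is 2.0017 (58 degrees of freedom), so t² = 4.0069. This corresponds to χ² = 60 × 4.0069 / (58 + 4.0069) = 3.877, against the usual 3.841. With 30 per arm no possible table falls between these two values, so the decisions never differ. Exact enumeration agrees:

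| | t-test on 0/1 | Uncorrected chi-square | Fisher's exact |
|---|---|---|---|
| 30 per arm, both rates 18% | 5.0% | 5.0% | 2.1% |
| 30 per arm, 18% vs 12% | 10.1% | 10.1% | 4.2% |
| 556 per arm, 18% vs 12% | 80.3% | 80.4% | not run |

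**Step 4. How much can the pilot say about the proportion?**

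Expected events: 30 × 0.18 = 5.4 and 30 × 0.12 = 3.6, on average 4.5 per arm. The approximate standard error of the risk difference is √(0.2532/30) = 0.092, so a simple 95% interval spans about ±1.96 × 0.092 = ±18 percentage points around a 6-point difference. That is wide, and the approximation is rough with so few events.

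**The case against.** The strongest reply is that little turns on this in a 60-patient feasibility pilot. Section 13 says an accurate sample size is not possible at this stage. Power to detect 18% versus 12% is about 4% to 10% under the proportion tests checked, so no confirmatory claim depends on the choice. A SAP may exist and may settle the method. This stands as a limit on the consequences. It does not remove the contradiction in the protocol text, which a SAP would have to override rather than fill in.

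A reader might also infer more than the documents support:

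- *That the planned test cannot estimate the stated outcome, or inflates the type I error.* On a 0/1 code it does estimate the risk difference, and it rejects at 5.0% when both rates are 18%. The harm depends on the ICU-days reading.
- *That the pilot then could not inform the main-trial design.* The event count per arm is observed whichever test is run, and nothing in Section 16 prevents its being tabulated. The most that can be said is that the planned analysis does not itself supply the risk difference and its interval.
- *That mean days would mislead more often than the proportion.* The protocol gives no distribution of ICU stay, so any such rate would rest on assumed inputs. Section 16 also allows a non-parametric test, which limits the influence of a few long stays.
- *That ICU length of stay is not collected.* It is already a secondary economic outcome. It is only absent from the clinical list.
- *That the proportion must be the primary outcome.* The hypothesis in Section 4 is worded as duration, so the sponsor could resolve the conflict either way.

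**Conclusion.** The point holds as a contradiction in current text. Sections 2, 13 and 14 define and size the primary endpoint as a proportion, and Section 16 analyses it as continuous. On the natural reading, the result labelled primary would concern days and not the >3-day event. On the 0/1 reading the decision equals that of the uncorrected chi-square at 30 per arm, and the defect is one of labelling. The 1112 is sound as a two-proportion figure (1110 recomputed) and needs no change while the proportion stays primary. The arithmetic assumes 1:1 allocation and the protocol's own 18% and 12%. Because the definition of the primary endpoint and its assigned test disagree, they should be reconciled before analysis, even though the pilot's comparison will be descriptive.

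**What to change.** Rewrite the analysis paragraph of Section 16 so that:

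1. ICU stay >3 days is analysed as a proportion: event rate per arm and risk difference, with a 95% confidence interval by a method suited to about 4 to 5 expected events per arm. Newcombe or Miettinen–Nurminen intervals are examples. A chi-square or Fisher test may be added as supporting and descriptive at 60 patients.
2. The t-test or rank-test sentence applies to continuous secondary outcomes only.
3. ICU length of stay in days is listed in Section 14 as a separate secondary outcome, analysed on a scale that allows for skew (log scale or difference in medians).

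If the sponsor intends duration to be primary, as Sections 4 and 5.2 suggest, then redefine the primary outcome in Sections 2 and 14 and re-size the main trial in Section 13 on a difference in duration with its standard deviation.

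The first route costs one paragraph and one line in the outcome list, with no new data. The second needs a new main-trial calculation with inputs that the protocol does not now give.
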